#### **4.2.1 Eczema Area and Severity Index (EASI)**

Descriptive statistics (N, mean, SD, median, minimum and maximum) for the absolute EASI, change, and percent change from baseline will be tabulated by visit. Change will be computed as the timepoint score – baseline score. Percent change as  $100 * \text{change} \div \text{baseline}$ . A categorical summary of the number and percentage of subjects achieving a 75% or greater decrease in EASI will be provided by visit as well as those achieving the response at any post-baseline visit. Likewise, a categorical summary of the number and percent of subjects achieving a 50% or greater decrease in EASI will be provided. This categorical summary of the EASI will be conducted on both the Efficacy Population and the PP population, separately.

#### **4.2.1 Subject Pruritus Assessment (SPA)**

Descriptive statistics (N, mean, SD, median, minimum and maximum) for the absolute SPA, change, and percent change from baseline will be tabulated by visit. Change will be computed as the timepoint score – baseline score. Percent change as  $100 * \text{change} \div \text{baseline}$ .

baseline.

#### **4.2.2 Signs of Atopic Dermatitis (SAD)**

For each symptom (erythema, induration, lichenification, excoriation, exudation), the number and percentage of subjects with a score of 0 (none),  $\leq 1$  (None or Mild) and improved by at least 1 level from baseline will be tabulated by visit. This categorical summary for the SAD will be conducted on both the Efficacy Population and the PP population, separately.

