9. SELECTION AND WITHDRAWAL OF SUBJECTS

9.1. Subject Inclusion Criteria

Subjects must meet the following criteria to be eligible for participation in the study:

1. Able to comprehend and willing to sign an Informed Consent Form (ICF).
2. Male or non-pregnant, non-nursing female subjects ≥ 18 years old at the time of informed consent.
3. Subject must have diagnosis of AD according to the Hanifin and Rajka criteria.
4. Subject must have a diagnosis of moderate (PGA =3) or severe (PGA=4) AD for a period of ≥ 6 months prior to the first dose of study medication (Visit 2).
5. Subject Visit 1 photographs are approved for enrollment by the dermatology review panel.
6. Body surface area involvement must be between 2-20% (excluding scalp, face, palms of hands, soles of feet, groin and genitalia).
7. Subject must have an absolute neutrophil count (ANC) and a platelet count within normal limits
8. Subject must be willing to refrain from washing area of treatment or swimming for 6 hours after each treatment application with ATI-502.
9. Subjects must be willing to refrain from excess of sun exposure.
10. Subject is willing and able to follow all study instructions and be willing to attend all study visits.
11. Subject must refrain from participating in strenuous exercise that would cause profuse sweating for a period of 6 hours after each treatment application with ATI-502.
12. Subject must refrain from using moisturizers, emollients, and sunscreen on target AD treatment area for the duration of protocol therapy.
13. Be in good general health and free of any known disease state or physical condition which, in the investigator's opinion, might impair evaluation of the subject or which might expose the subject to an unacceptable risk by study participation.
14. If a woman of childbearing potential (WOCBP), must have a negative serum pregnancy test at Screening (Visit 1) and a negative urine pregnancy test at Baseline (Visit 2) and agree to: use a highly effective method of birth control for the duration of the study; not be planning a pregnancy during the study duration and use contraception for 30 days after last application of study medication.
15. Sexually active male subjects must agree to use a barrier method of contraception from the first application of study medication to at least 30 days after the last application of study medication.

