12. STUDY ASSESSMENTS

12.1. Physician's Global Assessment (PGA)

The PGA is the investigator's assessment of the average overall severity of subject's AD at a particular point in time. At every study visit, the investigator will assess the PGA using the scale below and report the one integer that best describes the average overall severity of each target evaluation area of AD per subject. One assessment will be conducted for each target treatment area.

Table 5: Physician's Global Assessment

PHYSICIAN'S GLOBAL ASSESSMENT	
Grade	Descriptor
0	Clear: No erythema or induration; no oozing/crusting; barely perceptible residual post-inflammatory hypo- or hyperpigmentation may be present
1	Almost Clear: Minimal light red erythema and/or induration; no oozing/crusting
2	Mild: Light red erythema with mild induration; no oozing/crusting
3	Moderate: Red erythema with moderate induration; oozing/crusting may be present
4	Severe: Bright or deep red erythema with severe induration; oozing/crusting present

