### **4.1 Study Population, Disposition, Baseline Characteristics, Medical History Concomitant Medications, Exposure and Protocol Violations**

#### **4.1.1 Analysis Populations**

Safety Population: Includes all subjects with at least one application of study medication. The Safety Population will be used for all safety analyses.

Efficacy Population: Includes all subjects with at least one application of study medication. The Efficacy Population will be used for all efficacy analyses.

Per-Protocol (PP) Population: Includes all subjects who completed Visit 6 (Week 8). The PP Population will be used for sensitivity assessments of key efficacy analyses.

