### **4.2 Efficacy Endpoints**

The baseline for all efficacy measures will be the last non-missing value collected on or before the date of the first application of study medication. Analyses of post-baseline data will be performed on observed (non-missing) data based on nominal visits as collected on the CRF.

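### SAP 4.2.2 sets no baseline condition on the SAD sign counts, so for lichenification, excoriation and exudation they mix subjects who never had the sign with subjects who improved

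*SAP*

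**What the plan says.** SAP 4.2.2 defines the SAD table in one sentence. For each of erythema, induration, lichenification, excoriation and exudation it calls for "the number and percentage of subjects with a score of 0 (none"), then a score of 1 or below, "and improved by at least 1 level from baseline will be tabulated by visit". The populations follow: "This categorical summary for the SAD will be conducted on both the Efficacy Population and the PP population, separately". SAP 4.1.1 defines the first of these as "Efficacy Population: Includes all subjects with at least one application of study medication", and the second as subjects who completed Visit 6. Neither is limited to subjects who had the sign at baseline. SAP 4.2 adds: "Analyses of post-baseline data will be performed on observed (non-missing) data based on nominal visits as collected on the CRF". The denominator is therefore the subjects observed at each visit.

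Entry severity is set in Protocol 9.1: "Subject must have a diagnosis of moderate (PGA =3) or severe (PGA=4) AD". Protocol 12.1, Table 5, describes grade 3 as "Moderate: Red erythema with moderate induration; oozing/crusting may be present". At grade 4, oozing or crusting is part of the description. Lichenification and excoriation appear in no PGA grade. Protocol 12.4 scores each sign from 0 to 3 in each target area at Visits 2 to 6, and no entry criterion sets a minimum for any sign. SAP 1.2 states the SAD objective as change from baseline after four weeks.

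**The concern.** A threshold count describes change only if everyone starts on the far side of the threshold. The SAP relies on this for the PGA: section 4.2.3 notes that a score of 1 or below is at least a two-grade improvement, because entry requires 3 or 4. SAD has no such floor. A subject can validly enter at PGA 3 with exudation 0, or with lichenification or excoriation at 0 or 1, and appear in the favourable counts at every visit without changing.

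The improvement count errs the other way. A subject at 0 can never improve by a level but stays in the denominator. The objective is change from baseline, and this table is the only SAD analysis in the SAP. With a single arm, no control group shows how much of a rate was already there at the start.

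**Working it through.** The plan gives no SAD rate to reproduce, so the check reads the sentence in each possible way and then applies simple arithmetic.

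**Step 1: does entry supply a floor?**
- *Erythema and induration:* both are in the PGA 3 and PGA 4 descriptors, so a score of 0 at entry is not expected. The point has little force here.
- *Exudation:* optional at PGA 3, part of the description at PGA 4. The point applies mainly to PGA 3 entrants.
- *Lichenification and excoriation:* absent from the PGA. Lichenification is part of one of four major Hanifin and Rajka criteria (Protocol Appendix 2), of which three suffice, so it is not mandatory.

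**Step 2: three readings of the SAP 4.2.2 sentence.**
1. *Three separate items.* The score-0 and ≤1 rates include unchanged subjects, and the improvement rate is diluted.
2. *Improvement joined to ≤1.* Unchanged subjects leave the ≤1 count. The score-0 rate is still inflated and the joined rate is diluted.
3. *Improvement governing the whole list* (the least natural reading). The inflation disappears, but subjects at 0 still cap every rate.

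**Step 3: arithmetic.** N = 30 is the planned size (SAP 4.4). The other inputs are assumptions: a is the share with the sign absent at baseline and staying absent, and r is the share of affected subjects who clear.

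- Score-0 rate, all subjects: a + (1 − a)r
- Score-0 rate among baseline ≥1: r
- Ceiling on improvement, all subjects: 1 − a

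The improved column assumes that nobody improves without clearing.

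| Absent at baseline | Score 0, r = 0 | Score 0, r = 1/3 | Baseline ≥1 only, r = 1/3 | Improved, all subjects, r = 1/3 | Ceiling on improvement |
|---|---|---|---|---|---|
| 3/30 | 10.0% | 12/30 = 40.0% | 9/27 = 33.3% | 9/30 = 30.0% | 27/30 = 90% |
| 6/30 | 20.0% | 14/30 = 46.7% | 8/24 = 33.3% | 8/30 = 26.7% | 24/30 = 80% |
| 9/30 | 30.0% | 16/30 = 53.3% | 7/21 = 33.3% | 7/30 = 23.3% | 21/30 = 70% |
| 12/30 | 40.0% | 18/30 = 60.0% | 6/18 = 33.3% | 6/30 = 20.0% | 18/30 = 60% |
| 15/30 | 50.0% | 20/30 = 66.7% | 5/15 = 33.3% | 5/30 = 16.7% | 15/30 = 50% |

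The same clearance among affected subjects (33.3%) thus appears as anything from 40.0% to 66.7% scoring 0, and from 30.0% down to 16.7% improved, depending only on who had the sign at entry.

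**Step 4: the ≤1 count with no change at all.** With 6 subjects absent and 6 mild at baseline, a separate ≤1 item shows (6 + 6)/30 = 40%. Joined to improvement, it shows 0/30.

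**The case against.** The strongest reply is that the share of subjects without a sign at a visit is a legitimate descriptive quantity. The SAP labels the counts as none, or none or mild. A reader might infer that the plan counts subjects who never had a sign as cleared. It does not say so, and uses no response language for SAD. That stands: the trouble arises when the rate is read as evidence on the objective, which is change.

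The table is by visit and SAD is scored at Visit 2 before the first application, so a baseline column may be printed. It would expose the no-effect case, but the SAP does not promise it. Nor do marginal percentages show which subjects moved.

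Protocol 14.1 also plans means and, where applicable, mean changes for SAD, and SAP 4.5 does not withdraw them. SAP 4.2.2 does not carry them forward, although the SAP keeps change summaries for EASI, SPA and BSA.

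It is also fair that the sentence is ambiguous and that one of its three possible counts is itself based on change. That narrows the inflation but does not remove the dilution.

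Finally, replacing every count with a restricted one would drop subjects who start at 0 and develop the sign on treatment, which matters in a study whose primary objective is safety and tolerability. The fix has to respect that.

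**Conclusion.** The point holds for lichenification and excoriation, and for exudation mainly among subjects entering at PGA 3. On every reading, subjects at 0 dilute the improvement rate. On all but the least natural reading, the score-0 rate is inflated. The ≤1 rate is inflated only if it is a separate item.

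The size cannot be determined, because neither document gives a baseline SAD distribution. The figures of 20% and 80% for 6 of 30 absent are an illustration and assume that those subjects stay at 0. A reader might infer that most subjects lack exudation at entry, or that the table must greatly overstate efficacy. The documents show only that such subjects can be enrolled, not how many there will be. A reader might also object that the five signs cannot be compared, but neither document plans such a comparison.

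The study is single-arm with no inferential statistics, and SAD is one of five secondary measures. This is a worthwhile correction to the SAP, not a threat to the study's primary purpose.

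**What to change.** In SAP 4.2.2:

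- State whether improvement by at least one level is a separate item or is joined to the ≤1 count.
- Keep the all-subject counts, with a baseline column for each sign.
- Add score 0 and improvement of at least one level among subjects with baseline ≥1, and score ≤1 among subjects with baseline ≥2, printing the number at risk per sign. In these subsets, reaching 0 or ≤1 already implies at least one level of improvement, so these counts do not depend on how the sentence is read.
- Add a baseline-to-visit shift table for each sign, so that signs newly appearing on treatment stay visible.
- State how scores from several target areas form one subject-level score. Without this rule, neither baseline subset can be programmed.

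The cost is SAP wording, a baseline filter and slightly more tables. The restricted denominators are smaller and differ by sign, so they should be read beside the all-subject counts.

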#### **4.2.3 Physician Global Assessment (PGA)**

The number and percentage of patients achieving a PGA score  $\leq 1$  (Clear or Almost Clear) as well as those with PGA score=0 (Clear) will be tabulated by visit. Scores of 1 or less represent at least a 2-grade improvement from the protocol inclusion criteria of PGA 3 or 4. This categorical summary of the PGA will be conducted on both the Efficacy Population and the PP population, separately.

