6.2. Secondary Outcome Measures

The secondary outcome measures for this study are to assess the following:

- Change from baseline in Physician Global Assessment (PGA) score following 4 weeks of treatment with ATI-502 Topical Solution, 0.46%
- Change from baseline in body surface area affected by atopic dermatitis following 4 weeks of treatment with ATI-502 Topical Solution, 0.46%.
- Change from baseline in Eczema Area and Severity Index (EASI) score following 4 weeks of treatment with ATI-502 Topical Solution, 0.46%.
- Change from baseline in the subjects Signs of Atopic Dermatitis (SAD) assessment following 4 weeks of treatment with ATI-502 Topical Solution, 0.46%.
- Change from baseline in Subjects Pruritis Assessment (SPA) score following 4 weeks of treatment with ATI-502 Topical Solution, 0.46%.

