14. STATISTICS

14.1. Statistical Methods

Safety and efficacy results will be summarized and presented by visit, with no inferential statistics presented. Parameters related to safety and tolerability will be treated as primary analysis variables. Efficacy parameters will be treated as secondary endpoints.

All data will be summarized by visit, with presentations based on the nature of the parameter. For binary data such as presence or absence of treatment-emergent adverse events, the incidence will be presented along with the overall number of subjects and percentages. External clinical laboratory and similar externally sourced data will be summarized as binary outcomes based on the determination of values beyond applicable normal ranges, and in some cases the assessment of clinical significance of deviations from normal ranges. For ordinal categorical data including efficacy data from PGA, EASI, SPA and SAD scores, and continuous data such as affected body surface area, summary statistics will be presented including N, mean, median, standard deviation, and standard error, by visit. Where applicable, the mean changes from baseline for ordinal categorical and continuous parameters will be presented by visit, along with N, median, standard deviation and standard error.

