### 1.2 Secondary Objectives

The secondary outcome measures for this study are to assess the following:

- Change from baseline in Physician Global Assessment (PGA) score following 4 weeks of treatment with ATI-502 Topical Solution, 0.46%
- Change from baseline in body surface area affected by atopic dermatitis following 4 weeks of treatment with ATI-502 Topical Solution, 0.46%.
- Change from baseline in Eczema Area and Severity Index (EASI) score following 4 weeks of treatment with ATI-502 Topical Solution, 0.46%.
- Change from baseline in the subjects Signs of Atopic Dermatitis (SAD) assessment following 4 weeks of treatment with ATI-502 Topical Solution, 0.46%.
- Change from baseline in Subjects Pruritus Assessment (SPA) score following 4 weeks of treatment with ATI-502 Topical Solution, 0.46%...

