### **4.5 Changes in/ Clarifications to the Conduct of the Study or Planned Analysis**

In addition to the EASI-75 planned in the protocol, an EASI-50 has been added.

Sensitivity assessments of key efficacy analyses was included that was not specified in the protocol.

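### The SAP never summarises PGA score or its change from baseline, although that change is a named secondary outcome; SAD has a smaller version of the same gap

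*SAP*

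**What the plan says.** Protocol 6.2 lists as a secondary outcome "Change from baseline in Physician Global Assessment (PGA) score following 4 weeks of treatment with ATI-502 Topical Solution, 0.46"%. SAP 1.2 repeats it and also lists "Change from baseline in the subjects Signs of Atopic Dermatitis (SAD) assessment following 4 weeks of treatment with ATI-502 Topical Solution, 0.46"%.

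Protocol 14.1 sets out how such data are to be reported. It begins "For ordinal categorical data including efficacy data from PGA, EASI, SPA and SAD scores", adds continuous data such as body surface area, and states that "summary statistics will be presented including N, mean, median, standard deviation, and standard error, by visit". It continues: "Where applicable, the mean changes from baseline for ordinal categorical and continuous parameters will be presented by visit", together with N, median, SD and SE. Protocol 14.2 then lists the responder proportions, including two for PGA, in a section of their own.

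For PGA, SAP 4.2.3 plans the number and percentage at grade 1 or below, "Clear or Almost Clear) as well as those with PGA score=0 (Clear) will be tabulated by visit". It adds that a score of 1 or less amounts to an improvement of at least two grades, given the entry requirement of PGA 3 or 4. For SAD, SAP 4.2.2 plans counts per sign: score 0, score of 1 or less, and "improved by at least 1 level from baseline will be tabulated by visit".

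SAP 4.5 declares two changes from the protocol. One is the sensitivity assessments; the other reads "In addition to the EASI-75 planned in the protocol, an EASI-50 has been added".

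**The concern.** The named PGA outcome is a change in score. The planned PGA table reports only whether a subject reached a threshold, so it gives neither the size nor the direction of change among those who did not reach it. Partial improvement, no change and worsening cannot be told apart. In a 30-subject, single-arm, open-label study the descriptive tables are the whole efficacy result, so a secondary outcome that never appears in them as defined goes unreported. A reader comparing the report with the protocol would also find that a planned summary had disappeared without explanation.

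**Working it through.** **1. Planned against delivered.** The protocol gives no alpha, power or effect size, and SAP 4.4 says the 30 subjects have no formal statistical basis, so there is no stated figure to reproduce. The check is a comparison of protocol 14.1 with SAP 4.2, outcome by outcome.

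| Secondary outcome | Numeric summary in protocol 14.1 | Numeric score and change in SAP 4.2 | Counts in SAP 4.2 |
|---|---|---|---|
| PGA | Yes, named | None | Score <=1; score 0 |
| SAD | Yes, named | None | Per sign: 0; <=1; improved by >=1 level |
| EASI | Yes, named | Score, change, percent change | EASI-75, EASI-50 |
| SPA | Yes, named | Score, change, percent change | None |
| BSA | Yes, as continuous | Value, change, percent change | None |

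Two of the five secondary outcomes lack the numeric summaries, and neither omission is in SAP 4.5. The SAP cites protocol version 1.0, but the version 2.0 change list shows no revision to section 14, so the version difference does not explain the gap.

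**2. What the PGA counts pool.** Entry requires a baseline of 3 or 4, and the scale runs from 0 to 4. The pairs that are not <=1 at a visit are:

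- 3 to 2: change -1
- 3 to 3: change 0
- 3 to 4: change +1
- 4 to 2: change -2
- 4 to 3: change -1
- 4 to 4: change 0

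Changes from -2 to +1 therefore share one category.

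**3. Illustration for the mean PGA change (assumed data, not a forecast).** Take N = 30, one PGA value per subject, all at baseline 3, and r responders who reach grade 1 (change -2).

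- All non-responders improve one grade: mean = (-2r - (30 - r))/30
- All non-responders unchanged: mean = -2r/30

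| r | Share <=1 | Non-responders one grade better | Non-responders unchanged | Gap = (30 - r)/30 |
|---|---|---|---|---|
| 3 | 10% | (-6 - 27)/30 = -1.1 | -6/30 = -0.2 | 0.9 |
| 6 | 20% | (-12 - 24)/30 = -1.2 | -12/30 = -0.4 | 0.8 |
| 12 | 40% | (-24 - 18)/30 = -1.4 | -24/30 = -0.8 | 0.6 |

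With r = 6, 12 non-responders unchanged and 12 worsening from 3 to 4, the mean is (-12 + 12)/30 = 0.0. All three r = 6 cases print the same row: 6/30 at <=1 and 0/30 clear.

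With half the subjects and half the responders at baseline 4, r = 6 gives three changes of -2 and three of -3, a sum of -15. The means are (-15 - 24)/30 = -1.3 and -15/30 = -0.5. The gap is again 0.8, because it equals the non-responder share times one grade whatever the baseline mix.

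**4. SAD.** Each sign is graded 0 to 3, giving 4 x 4 = 16 possible baseline-visit pairs: 6 improve, 4 are unchanged and 6 worsen. If the improvement count stands alone, the 6 improving pairs are counted together whatever their size. If SAP 4.2.2 means a score of <=1 and improvement jointly, which its wording allows, only 5 qualify because 3 to 2 drops out. On either reading, unchanged and worsened subjects are not separated. These are counts of possibilities, not probabilities.

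**The case against.** The best defence is that PGA change is reported, only in dichotomised form. Protocol 14.2 names PGA <=1 with a two-grade improvement and PGA 0 as responder criteria, SAP 4.2.3 delivers both, and for baselines of 3 or 4 a score of <=1 does imply a fall of at least two grades. Preferring counts to means on a five-point ordinal scale is defensible, and protocol 14.1 opens its sentence on mean changes with a qualifier about applicability. For SAD, the one-level improvement count is a change measure, and the by-visit counts of 0 and <=1 would show net movement.

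Much of this is fair, but it does not close the gap. The qualifier covers only the change sentence, not the by-visit score summaries, and change in PGA score is itself a named outcome, so it is hard to call inapplicable. The responder proportions stand in a separate section of the protocol and do not replace the 14.1 summaries. The ordinal argument is not one the plan makes: protocol 14.1 classes EASI and SPA with PGA as ordinal, and the SAP gives means for both. The SAD defence does stand in part, which is why SAD is the lesser point.

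Two further objections are correct but limited. Protocol 12.1 calls for one PGA per target area, so one value per subject is a simplification in the illustration; the SAP's own counts also leave open how areas are combined. The scenarios are deliberately extreme and show what the table cannot distinguish, not what will happen. SAP 4.3 mentions a separate document, but describes it as data handling and programming specifications; nothing says it adds efficacy summaries.

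**Conclusion.** The concern holds. If the SAP is followed exactly, the PGA secondary outcome is not reported as defined, the summaries promised in protocol 14.1 are absent for PGA and SAD, and the departure is undeclared. Under the stated assumptions, one identical PGA row with 20% responders covers mean changes from -1.2 to 0.0. For responder shares of 10% to 40%, the gap between non-responders all improving one grade and all unchanged is 0.9 to 0.6 of a grade. Confidence is high on the mismatch between the documents; the figures only illustrate the information lost.

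The consequence is limited to descriptive reporting. Safety is primary, nothing inferential is planned, no error rate or sample size is affected, and EASI, SPA and BSA keep numeric change summaries. It should be fixed because a named outcome is involved and the cost is very small.

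**What to change.** - **SAP 4.2.3:** add by-visit N, mean, SD, SE, median, minimum and maximum for PGA score and for change from each subject's recorded baseline, optionally with a baseline-by-visit shift table. Label Week 4 (Visit 5) as the timepoint of the secondary outcome. SE is included because protocol 14.1 lists it; the SAP also omits it for EASI, SPA and BSA, so a single decision could cover all five.
- **SAP 4.2.2:** add the same score and change summaries, or a shift table, for each SAD sign. Leave out percent change, which is undefined when a sign is 0 at baseline. That can occur, since oozing or crusting is optional in the PGA 3 descriptor. State whether the <=1 and improvement criteria are separate or joint.
- **Both sections:** state how several target areas are combined into one subject value, and use the same rule for the counts.
- Keep the planned categorical counts.
- **SAP 4.5:** if either numeric summary is left out on purpose, record that and give the reason.

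The cost is a few sentences in the SAP and a few descriptive tables from data already collected. No new data are needed.

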
Statistical methods:
 
Safety and efficacy results will be summarized and presented by visit, with no inferential statistics presented. Parameters related to safety and tolerability will be treated as primary analysis variables. Efficacy parameters will be treated as secondary endpoints.
 
All data will be summarized by visit, with presentations based on the nature of the parameter. For binary data such as presence or absence of treatment-emergent adverse events, the incidence will be presented along with the overall number of subjects and percentages. External clinical laboratory and similar externally sourced data will be summarized as binary outcomes based on the determination of values beyond applicable normal ranges, and in some cases the assessment of clinical significance of deviations from normal ranges. For ordinal categorical data including efficacy data from PGA, EASI, SPA and SAD scores, and continuous data such as affected body surface area, summary statistics will be presented including N, mean, median, standard deviation, and standard error, by visit. Where applicable, the mean changes from baseline for ordinal categorical and continuous parameters will be presented by visit, along with N, median, standard deviation and standard error.

Analysis of Efficacy Outcome Measures:
 
Subject responder analyses will be conducted, by visit, based on the following criteria:
 
• The proportion of subjects whose active-treated lesions are judged to be clear or near clear on the PGA (PGA = ≤ 1) with a 2 grade or greater improvement from a baseline score of PGA=3 or PGA =4;• The proportion of subjects whose active-treated lesions are judged to be clear on the PGA (PGA = 0);

- The proportion of subjects who had an improvement from baseline of at least 75% in EASI score (EASI – 75).

Other subject responder criteria will be established as appropriate from data observation and the results will be presented as above.

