14.2. Analysis of Efficacy Outcome Measures

Subject responder analyses will be conducted, by visit, based on the following criteria:

- The proportion of subjects whose active-treated lesions are judged to be clear or near clear on the PGA (PGA = ≤ 1) with a 2 grade or greater improvement from baseline;
- The proportion of subjects whose active-treated lesions are judged to be clear on the PGA (PGA = 0);
- The proportion of subjects who had an improvement from baseline of at least 75% in EASI score (EASI – 75).

Other subject responder criteria will be established as appropriate from data observation and the results will be presented as above.

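### SAP 4.2.3 counts PGA ≤1 alone and infers the protocol's 2-grade improvement from the entry criteria; the rules differ only for subjects treated with a baseline below 3, where the SAP can only overcount

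*SAP*

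**What the plan says.** **Protocol definition.** Section 14.2 counts a subject as a responder at PGA ≤1 "with a 2 grade or greater improvement from baseline". The synopsis is narrower: the improvement must be "with a 2 grade or greater improvement from a baseline score of PGA=3 or PGA =4".

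**SAP definition.** Section 4.2.3 tabulates by visit "The number and percentage of patients achieving a PGA score" of 1 or less and, separately, of 0. No change from baseline is computed. In its place stands the sentence "Scores of 1 or less represent at least a 2-grade improvement from the protocol inclusion criteria of PGA 3 or 4".

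**SAP baseline.** Section 4.2 states: "The baseline for all efficacy measures will be the last non-missing value collected on or before the date of the first application of study medication". PGA is scheduled at Visits 1 and 2, and the first dose is given in clinic at Visit 2. Baseline is therefore normally the Visit 2 score, with Visit 1 as the fallback.

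**SAP analysis sets.** Section 4.1.1 reads: "Efficacy Population: Includes all subjects with at least one application of study medication". The Per-Protocol set is everyone who completed Visit 6. Neither set has a condition on baseline PGA. Section 4.1.8 has entry violations identified and listed, with no exclusion. Section 4.5, which records changes from the protocol, names EASI-50 and the sensitivity assessments but not the PGA rule.

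**Entry rules.** Inclusion criterion 4 (protocol 9.1) reads "Subject must have a diagnosis of moderate (PGA =3) or severe (PGA=4) AD for a period of ≥ 6 months" before the first dose. Protocol 7.1 and SAP 2 require a PGA score of 3 or 4. The schedule of assessments has inclusion and exclusion checked at both Visit 1 and Visit 2. Protocol 11.1 requires target areas to meet the entry criteria, PGA 3 or 4 among them, at both visits.

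**The concern.** The SAP measures improvement against the entry rule, whereas the protocol measures it against the subject's own baseline. The two agree only if every analysed subject has a baseline of 3 or 4, and nothing in the SAP makes that so. Its baseline is whatever was scored before dosing, both analysis sets keep subjects who failed an entry criterion, and the violation review produces only a listing. The SAP thus provides for entry violations in 4.1.8 and assumes none bear on PGA in 4.2.3. Running the PGA summary on the Per-Protocol set does not help, because that set depends on completing Visit 6 and not on eligibility.

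What is at stake is whether the reported PGA response rate is the one the protocol defined. A subject at PGA 2 before dosing who is later scored 1 would be reported as a responder after a 1-grade change. The inferential sentence is also the only place where SAP 4.2.3 relates PGA results to baseline, although change from baseline in PGA is a secondary objective (SAP 1.2).

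**Working it through.** There is no planned figure to reproduce. SAP 4.4 gives N = 30 without a formal basis, and protocol 14.1 rules out inferential statistics. The check is an enumeration.

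**Inputs.** PGA scale 0 to 4 (protocol Table 5); planned N = 30 (SAP 4.4). For baseline b and visit score p, the three rules are:

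- SAP 4.2.3: p ≤ 1
- Protocol 14.2: p ≤ 1 and b − p ≥ 2
- Synopsis: p ≤ 1, b − p ≥ 2 and b = 3 or 4

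**Step 1: all 25 pairs (b, p).** Only p = 0 or 1 can satisfy any rule.

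| Baseline b | SAP responders (p) | Protocol 14.2 (p) | Synopsis (p) | Counted by SAP but not by 14.2 |
|---|---|---|---|---|
| 4 | 0, 1 | 0, 1 | 0, 1 | none |
| 3 | 0, 1 | 0, 1 | 0, 1 | none |
| 2 | 0, 1 | 0 | none | 2→1 |
| 1 | 0, 1 | none | none | 1→1, 1→0 |
| 0 | 0, 1 | none | none | 0→1, 0→0 |

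At baseline 3 or 4 all three rules agree. Below 3, five pairs are counted by the SAP and not by 14.2. Against the synopsis there are six, the extra one being 2→0. No pair is counted by either protocol rule and missed by the SAP, so any discrepancy is an overcount.

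**Step 2: size per subject.** k misclassified subjects raise the rate by k/30:

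- k = 1: 1/30 = 3.3 points
- k = 2: 2/30 = 6.7 points
- k = 3: 3/30 = 10.0 points

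As an illustration only, suppose the SAP rule gives 9/30 = 30.0%. With one misclassified subject the protocol rate is 8/30 = 26.7%; with two it is 7/30 = 23.3%. The 9 is an assumption; the documents contain no response rate. The unit is 1/N, so it shifts somewhat if the number observed at a visit is not 30.

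**Step 3: could a low baseline occur?** The documents give no share of subjects with a baseline below 3. For an assumed share q, the chance of at least one among 30 is 1 − (1 − q)^30:

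| Assumed q | Chance of at least one low baseline |
|---|---|
| 1% | 26.0% |
| 3% | 59.9% |
| 5% | 78.5% |
| 10% | 95.8% |

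This is not the chance of a misclassified responder, which is smaller. The subject must also be scored ≤1 later and, for a baseline of 2 under Section 14.2, exactly 1.

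**The case against.** The SAP gives its reason openly, and for anyone who meets the entry criteria its arithmetic is right. Only subjects dosed in breach of those criteria are affected, and the protocol has several barriers against that. It requires a PGA of 3 or 4 (7.1), rechecks eligibility at Visit 2, and applies the PGA requirement to target areas at both pre-dose visits (11.1). The sponsor's violation review (SAP 4.1.8) should show any subject dosed at PGA 2. The study is open-label, single-arm and descriptive, with safety as its primary outcome. All of this stands, and it makes the point minor. It does not remove it: a listing makes a low baseline visible but does not correct the tabulated rate.

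A reader might go further and infer that low baselines are likely, because criterion 4 is worded as a diagnosis over 6 months, screening may last 14 days, and protocol 5.1 describes spontaneous remission. The documents do not support that. The Visit 2 recheck falls at the end of the screening interval, and Section 5.1 also says that moderate to severe disease seldom clears untreated. Nor may the shares or rates in the working be read as forecasts; they are assumptions.

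A fair further objection is that restoring the 14.2 condition alone would still count a change from 2 to 0, which the synopsis excludes. That stands, and the fix below deals with it. Also, PGA is scored for each target area (protocol 12.1) and the SAP has no rule for combining areas into one score per subject. That gap is a separate matter and affects the SAP's present rule equally, but a computed change depends on it too.

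**Conclusion.** The mismatch is real and narrow. SAP 4.2.3 replaces a computed condition with an inference that holds exactly for baselines of 3 or 4 and fails below 3. Since neither efficacy analysis set removes such subjects, the tabulated rate can exceed the protocol's, by 3.3 points per misclassified subject at N = 30, and can never fall short of it. The number of such subjects is unknown and may be zero, in which case the result is unchanged.

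The documents do not support reading this as a general inflation of the PGA response rate, or as a problem for eligible subjects. The conclusion rests on one score per subject and on baseline as SAP 4.2 defines it. The correction is minor and concerns one descriptive secondary tabulation. No error rate or power is involved.

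**What to change.** In SAP 4.2.3, define the PGA responder at a visit by all of the following:

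- visit PGA ≤1;
- baseline PGA minus visit PGA ≥2, with baseline as in SAP 4.2;
- baseline PGA of 3 or 4, which brings Section 14.2 into line with the synopsis.

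State that subjects with a lower baseline count as non-responders and stay in the denominator. The third condition makes the second automatic, but writing both keeps the protocol's condition explicit. The separate tabulation of PGA = 0 needs no change, because the protocol attaches no improvement condition to it.

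Delete the sentence that infers the 2-grade change from the inclusion criteria. If PGA ≤1 alone is kept as an additional tabulation, record it in SAP 4.5 as a change from the protocol. Subjects with a baseline below 3 can be identified in the violation listing already planned in SAP 4.1.8, so no new output is needed.

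The cost is a few lines of SAP text and a short change to the program. All the data are already collected, and the result is identical if every baseline is 3 or 4.
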